8.10	Reporting urgent safety measures	28
8.11	Additional definitions for safety reporting in medical device trials	28
9. STA	ATISTICAL ANALYSES	28
9.1	Planned recruitment rate	30
9.2	Statistical analysis	30
9.3	General principles	30
9.4	Adaptive analyses	30
9.5	Primary Estimand for Adaptive and Final Analysis	32
9.6	Primary Modelling Approach for Adaptive and Final Analysis	32
10. REC	GULATORY, ETHICAL AND LEGAL ISSUES	34
10.1	Declaration of Helsinki	34
10.2	Good Clinical Practice	34
10.3	Ethics Committee Approval	34
10.4	Regulatory Authority Approval	35
10.5	Non-Compliance and Serious Breaches	35
10.6	Insurance and Indemnity and Sponsor	35
10.7	Trial Registration	35
10.8	Informed Consent	35
10.9	Participant Confidentiality	35
10.10	Data Protection and Participant Confidentiality	36
10.11	End of Trial	36

Confidential Page 7 of 48

10.12	Study Documentation and Data Storage	36
11. DA	TA MANAGEMENT	36
11.1	Source Data	36
11.2	Language	37
11.3	Database	37
11.4	Data Collection	37
11.5	Archiving	37
12. ST	UDY MANAGEMENT STRUCTURE	37
12.1	International Trial Steering Committee	38
12.2	International Trial Management Group	38
12.3	Data Monitoring Committee	38
12.4	Early Discontinuation of the Study	38
12.5	Risk Assessment	38
12.6	Monitoring	38
12.7	Quality Control and Quality Assurance	39
12.8	Peer review	39
12.9	Public Involvement	39
12.10	Publication and Dissemination policy	40
REFER	ENCES	42
13. RE	VISION HISTORY	43
	RE PAGE 2 (SPONSOR)	45
	RE PAGE 3 (STATISTICIAN) RE PAGE 4 (PRINCIPAL INVESTIGATOR)	46 47
APPENDI	,	48

Confidential Page 8 of 48

Protocol No: 175151 V 2.1 30.07.2025 Sponsor: Imperial College

London

TRIAL SUMMARY

TITLE: Precision medicine Adaptive Network platform Trial in Hypoxaemic acutE respiratory failuRe (PANTHER)

OBJECTIVES

To accelerate the development of pharmacological therapies for critical illness by establishing an international phase 2 precision medicine adaptive platform trial to test the efficacy of prioritised pharmacological interventions in critically ill patients, including acute respiratory distress syndrome (ARDS) and pandemic infection, subphenotypes.

PHASE: 2

DESIGN

A multicentre, allocation concealed, randomised, open-label Bayesian adaptive multi-arm platform trial with pre-defined triggers for efficacy and futility stopping (as compared to usual care). The trial will stratify participants by biological markers into different subphenotypes. Initial stratification will be into hyperinflammatory and hypoinflammatory subphenotypes in ARDS based on plasma biomarker profiles. Regular adaptive analyses will enable efficient identification of treatment effects within each subphenotype, stopping interventions where there is evidence of efficacy or futility, and bringing in new interventions and new subphenotypes.

SAMPLE SIZE

As a platform trial the sample size is not fixed. Pre-defined statistical triggers for efficacy and futility determine the stopping of interventions and the replacement by new interventions. The initial maximum number to be recruited globally per intervention for hypoinflammatory patients is 504 and for hyperinflammatory patients it is 529. Usual care is not limited by a maximum sample size and will recruit for the duration of the trial.

INCLUSION/EXCLUSION CRITERIA

Inclusion criteria

- 1) Critically ill patients in hospital and at least 1 of the following:
 - a) Acute respiratory distress syndrome (ARDS)*
 - b) A pandemic associated syndrome (this will be triggered if a new pandemic is declared)

*ARDS as defined by

- (i) a known acute clinical insult or new or worsening respiratory dysfunction, and
- (ii) receiving respiratory support via invasive mechanical ventilation or non-invasive ventilation including continuous positive airway pressure, or high-flow nasal oxygen ≥30L/min and
- (iii) Within the same 24-hour time period:
 - bilateral opacities on chest imaging not fully explained by effusions, lobar/lung collapse/atelectasis, or nodules, and
 - respiratory failure not fully explained by cardiac failure, fluid overload, pulmonary embolism, acute airways disease, or interstitial lung disease and,
 - PaO2/FiO2 ratio <40 kPa from arterial blood gases, or SpO2/FiO2 <315 from pulse oximetry where SpO2 <97.

Confidential Page 9 of 48

Protocol No: 175151 V 2.1 30.07.2025 Sponsor: Imperial College

London

The time of onset of ARDS is when the last criterion in (iii) is met.

Exclusion criteria

Platform level:

- (a) >48 hours from diagnosis of ARDS
- (b) Planned withdrawal of life-sustaining treatment within the next 24 hours
- (c) Previous enrolment in the PANTHER trial in the last 12 months
- (d) Declined consent

Additional intervention-specific exclusion criteria will apply which are detailed in each intervention-specific appendix.

TREATMENT/MAIN STUDY PROCEDURES (including treatment duration and follow-up). Therapeutic interventions will be compared with usual care within each subphenotype (see intervention appendices). We will start the platform with 2 interventions and usual care. Additional therapeutic interventions can enter the trial by replacing the initial interventions when they reach criteria for efficacy, for futility, or the maximum sample size or if the scope of the platform expands.

OUTCOME MEASURES

PRIMARY ENDPOINT

28-day organ support-free days, incorporating mortality as a composite on an ordinal scale. Organ support is defined as needing either respiratory or cardiovascular support.

SECONDARY ENDPOINT(S)

- 28-day vasopressor-free days
- 28-day respiratory support-free days ii.
- Receiving new renal replacement therapy iii.
- Progression to invasive mechanical ventilation, extracorporeal membrane İ۷. oxygenation or death among those not receiving that support at baseline
- ICU length of stay ٧.
- Hospital length of stay νi.
- All-cause mortality at 28 and 90 days, vii.
- Safety outcomes (as defined in secondary endpoint section 3.5) viii.
- Serious adverse events ix.
- Physical function (SPPB) at hospital discharge (up to 1 week prior to discharge) Χ.
- Cognitive function (MoCA) at hospital discharge (up to 1 week prior to discharge) χi.

If it is not possible to collect physical function and cognitive impairment measures prior to hospital discharge, this will not be a protocol deviation.

TERTIARY ENDPOINT(S)*

- 14-day delirium and coma free days i.
- Incidence of ICU acquired weakness (MMST and hand grip strength dynamometry ii. and maximal inspiratory pressure) at day 7 and ICU discharge
- Health-related quality of life, (EQ-5D-5L) at 90 days and 180 days iii.
- Hospital Anxiety and Depression Scale (HADS) at 90 days and 180 days ίV.
- Social and Wellbeing (SF-36) at 90 days and 180 days ٧.

Confidential Page 10 of 48

	Protocol No: 175151	Sponsor:	Imperial	College	V 2.1 30.07.2025
		London			
PANTHER					

vi. Impact of Events Scale (6 item) at 90 days and 180 days

vii. Care and wellbeing needs at 90 days and 180 days

viii. Cognitive function (MoCA) at 90 days and 180 days

PHENOTYPING

Initial subphenotypes will be the hyper and hypoinflammatory subphenotypes described in ARDS.

Over time additional / alternative biomarkers to determine subphenotypes may be added.

Confidential Page 11 of 48

^{*}Not all sites are expected to collect these endpoints

London

PROTOCOL STRUCTURE

The structure of this protocol differs from that of a conventional trial due to the trial's adaptive nature. These adaptations are specified using a modular protocol structure.

The master protocol contains information about the general conduct of the platform. Detailed information about the interventions, approaches to subphenotyping, statistical methods and regional specific governance are detailed in separate appendices. The structure of the protocol allows for the addition of a pandemic appendix which would describe how the platform could recruit in the setting of a pandemic.

1.1 **Master Protocol**

This document acts as the master protocol for the entire platform. It contains all information that is generic to the trial irrespective of the regional location in which the trial is conducted and the interventions being tested.

The protocol has the following additional appendices:

1.2 Intervention Specific Appendices

These will be separate appendices providing information specific to each intervention. Each intervention specific appendix will be submitted to Ethics and local Regulatory Authority prior to commencement. Each intervention specific appendix will include:

- Background of the intervention
- Inclusion/exclusion criteria specific to the intervention
- Delivery of the intervention
- Any intervention specific reporting (including safety)

1.3 Region Specific Appendices

PANTHER is an international trial and will be conducted in various geographical locations. As such, region-specific appendices will include all information required to conduct the trial in a specific region. This will enable the addition of new regions or changes to existing ones without the need to amend the master protocol. The region-specific appendix should be submitted for ethics and regulatory review alongside the master protocol and all other relevant appendices. The region-specific appendix will include:

- Definition of the region
- Organisation of trial management of the region
- Ethical and regulatory considerations

1.4 Statistical Analysis Appendix

This will describe in detail the statistical analyses to be conducted during PANTHER as well as the final analyses after any intervention meets a stopping

Confidential Page 12 of 48

rule. It will be updated as required when new interventions or subphenotypes are added.

1.5 Statistical Design Appendix

This appendix will describe the design and simulation study to examine the trial operating characteristics. The trial uses a Bayesian analysis framework, and the design is centred around the selection of optimal stopping rules over the range of potential trial results balancing power and type I error alongside sample size. The statistical design appendix will be updated as the trial progresses and changes may be necessary e.g. in response to the addition of new interventions or new subphenotypes such that the outcome rate or subphenotype proportion in the population differs.

1.6 Subphenotype Appendix

This appendix will describe how subphenotypes will be identified and which devices will be used in the process.

2. BACKGROUND

Critical illness is characterised by life-threatening organ dysfunction caused by a dysregulated host response to an acute insult including infection and trauma, which has significant patient burden and is a major healthcare problem. For those that survive, it can be life-changing, with long term physical and psychological consequences.

Critically ill patients are described in both clinical practice and research according to clinical syndromes, such as Acute Respiratory Distress Syndrome (ARDS). ARDS is characterised by non-cardiogenic pulmonary oedema (identified by opacities on chest X-ray). ARDS affects all age groups, has a high mortality of up to 30-50% and causes a long-term reduction in quality of life for survivors (1, 2). ARDS has significant resource implications in terms of ICU and hospital stay. The delivery of critical care to patients with ARDS accounts for a significant proportion of ICU capacity. In addition, survivors often have long-term physical and cognitive impairment requiring support in the community and many survivors are unable to return to work 12 months after hospital discharge (3-5). The high incidence, mortality, long-term consequences and high economic cost mean that ARDS is an extremely important problem.

There are currently no proven pharmacological treatments for ARDS (outside of COVID-19), other than general supportive therapies and treating the underlying insult. There is significant clinical and biological heterogeneity within critical illness syndromes which has contributed to the failure to date to translate pre-clinical research into effective therapies. Using syndromic definitions does not provide information on which subgroups of patients are likely to respond effectively and safely to a given pharmacological treatment.

A new paradigm in critical care suggests that de-emphasising clinical syndromic definitions and focusing on subphenotypes more closely linked to the host biological response is the key to identifying effective therapeutics (6), which remains a significant area of unmet need. Considerable recent progress has been made towards identifying biological

Confidential Page 13 of 48

subphenotypes in patients with ARDS, which appear to respond differently to specific interventions in secondary analysis of completed randomised controlled trials (7–9).

Developing effective pharmacological therapies for ARDS will improve patient outcomes in an area of significant unmet need as well as reducing costs. Survivors of ARDS experience reduced health-related quality of life, with substantial health care and societal costs. Resolution of lung injury is a predictor of less long-term disability in ICU survivors (4). Therefore, effective pharmacological therapies that hasten the resolution of ARDS may also enhance quality of life for ARDS survivors.

In summary, ARDS is a life-threatening condition with high mortality rates and there are no proven pharmacological treatments outside of ARDS caused by COVID-19. Given this landscape of high mortality, biological plausibility, and lack of effective therapies, there is a scientific rationale to repurpose agents with proven safety profiles in critically ill patients outside their licensed indications and prescribing restrictions.

Precautions on use of potential therapies are often derived from chronic use contexts in non-life threatening conditions, not the short-term, high-mortality setting of ARDS. In ARDS, where there is high unmet need, the risk-to-benefit balance likely differs dramatically. The expected benefit (improved survival, reduced duration of organ support) may outweigh potential adverse effects, particularly in the setting where no other therapy exists. In contrast to chronic use where cumulative exposure risks are more relevant, short-duration therapy (or until ICU discharge) in a highly monitored ICU environment substantially mitigates those risks.

As part of routine care laboratory measurements, including liver enzymes, renal function, and full blood count, are regularly measured in patients in ICU. In addition, again as part of routine care, patients in ICU are monitored for signs of infection and antibiotics started where infection is suspected.

Finally where specific laboratory monitoring is required, eg creatine kinase and liver enzymes, these will be measured regularly as defined in the protocol with stopping rules for the IMP based on defined thresholds which have been used safely in the setting of trials of the critically ill. As a result of this clinical routine and protocol defined monitoring in ICU and anticipated risk-to-benefit balance these stopping rules may be more liberal to what has been described in the IMP SmPC for chronic use.

For similar justification, the investigator will use their clinical discretion to follow the guidance for the concomitant use of other drugs detailed in the 'special warnings and precautions for use' and 'interaction with other medicinal products' provided in the approved version of the IMP SmPC.

Restricting the use of IMPs based on licensing boundaries designed for other populations or long-term settings withholds potential benefit in a condition with high mortality and no proven pharmacological interventions. When paired with appropriate safety monitoring, their repurposing is justified and urgently needed.

This adaptive platform trial which stratifies critically ill patients based on their biological subphenotype, will enable a "precision medicine" approach to accelerate the development of pharmacological therapies for critical care.

Confidential Page 14 of 48

Protocol No: 175151 V 2.1 30.07.2025 Sponsor: Imperial College

London

Interventions

Interventions for the platform trial will be selected through a prioritisation process. Initial proposals have come from co-investigators. Over time, external clinical, academic or industry investigators may submit proposals.

Proposals are considered by the PANTHER intervention selection committee based on the existing evidence base, including safety and other pharmacological data, and also feasibility. This committee will then make recommendations to an independent intervention committee who will advise the platform trial management group who will make the final decision about inclusion into the platform. The Trial Steering Committee, Data Monitoring Committee and funder(s) will be informed of the plan to introduce a new intervention prior to the commencement of the intervention.

It is anticipated that new interventions will join the platform at intervals, as others reach criteria for efficacy, for futility, or the maximum sample size. Over time, the evidence supporting interventions is likely to evolve. Therefore, interventions deemed to have insufficient support at the time of assessment may continue to be periodically reconsidered.

Details of each intervention, including rationale, pharmacological information, specific inclusion / exclusion criteria, dose, duration and other intervention specific information are provided in separate intervention appendices.

2.2 Subphenotypes

Multiple approaches to identify subphenotypes of clinical syndromes in critically ill patients have been proposed. These subphenotypes may also determine differential treatment effect. In order to assess treatment response by subphenotype, in this platform subphenotype will be determined prior to randomisation.

Initially the platform will use the hyper and hypoinflammatory subphenotypes previously described in ARDS. More detail about these subphenotypes and how they will be determined in the platform, including devices used, is contained in a separate appendix. It is expected that additional subphenotypes, using different biological samples and devices will be added over time.

3. OBJECTIVES AND ENDPOINTS

Primary Objective 3.1

To accelerate the development of pharmacological therapies for critical illness by establishing an international phase 2 precision medicine adaptive platform trial to test the efficacy of prioritised pharmacological interventions in patients with ARDS and pandemic infection.

3.2 Secondary Objective

To develop an infrastructure for identifying, developing and testing additional subphenotypes and therapies for critical illness in the ongoing platform trial.

Confidential Page 15 of 48

London

3.3 Tertiary Objective

Additional objectives are to establish an ongoing platform trial that:

- plays a leading role in international collaborative research efforts.
- provides a vehicle for early career investigators to build clinical trial capacity.
- can facilitate collaboration with commercial partners to test promising innovative therapies for critical illness.
- is sustainable through a combination of academic and commercial funding opportunities.
- can collect samples and data on other precision medicine factors.
- can rapidly pivot in the event of a new pandemic of a pathogen associated with respiratory failure, providing pandemic preparedness infrastructure.

3.4 Primary Endpoint

Primary endpoint: 28-day organ support-free days, incorporating mortality.

This is a composite ordinal scale outcome. All deaths are scored "-1" on the ordinal scale, i.e., the worst outcome. Then to assess important changes in outcome for surviving participants, the number of days free of organ support up until day 28 is calculated, so that a high score is good as it corresponds to a quicker recovery. Organ support is defined as needing either respiratory or cardiovascular support. Respiratory support is defined as invasive mechanical ventilation or non-invasive ventilation including continuous positive airway pressure or high-flow nasal oxygen with an FiO2 ≥ 0.4 and a flow rate ≥30L/min. Cardiovascular support is defined as the continuous infusion of any vasopressor or inotrope medication.

Being free of organ support is defined as the last time receiving support and does not require a specified time period to define success.

3.5 Secondary Endpoints

- 28-day vasopressor-free days i.
- 28-day respiratory support-free days ii.
- lii. Receiving new renal replacement therapy
- iv. Progression to invasive mechanical ventilation, extracorporeal membrane oxygenation or death among those not receiving that support at baseline
- ICU length of stay ٧.
- vi. Hospital length of stay
- vii All-cause mortality at 28 and 90 days
- viii. Safety outcomes:-
 - Elevated Creatine Kinase more than 10 times the upper limit of normal
 - Alanine Transaminase or Aspartate Transaminase more than 8 times the upper limit of normal
 - Severe thrombocytopenia, out of keeping with clinical disease
 - Severe neutropenia, out of keeping with clinical disease
 - Serious infection defined as a positive blood cultures requiring treatment and pulmonary aspergillosis requiring treatment
 - Venous thromboembolism
 - Stroke
 - Myocardial infarction

Confidential Page 16 of 48

	Protocol No: 175151	Sponsor:	Imperial	College	V 2.1 30.07.2025
	1 1010001110. 110101	London	mpona	ooogo	7 2.1 00.07.2020
		London			
PANTHER					

- Ischaemic bowel
- Gastrointestinal perforation
- Clinically important gastrointestinal (GI) bleeding. Defined as overt bleeding on GI endoscopy, developing as a complication in the ICU and accompanied by 1 or more of the following features within 24 hours:-
 - Spontaneous drop of systolic, mean arterial pressure or diastolic blood pressure of 20mmHg or more
 - o Start of vasopressor or a 20% increase in vasopressor dose
 - Decrease in haemoglobin of at least 2 g/dl
 - o Transfusion of 2 unites of packed RBC or more
- ix. Serious adverse events
- x. Physical function (SPPB) at hospital discharge (up to 1 week prior to discharge)
- xi. Cognitive function (MoCA) at hospital discharge (up to 1 week prior to discharge)

If it is not possible to collect physical function and cognitive impairment measures prior to hospital discharge, this will not be a protocol deviation.

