8.6 Adverse Event recording

As this is a trial is conducted in critically ill patients with life-threatening critical illness then adverse events are expected to occur regularly in most, if not all, patients regardless of treatment assignment. Events that that are expected in this population i.e. events related to the underlying critical illness will not be reported as adverse events. In addition, unless an adverse event is assessed to meet Serious Adverse Event criteria these adverse events will not be reported in the case report form and simply noted in the patient's local medical record. Any additional reporting will be detailed in the RSA and ISA.

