8.8 Serious Adverse Events (SAE)

(i) Definition of SAE

An SAE is defined as any event that

- Results in death:
- Is life-threatening*;
- Requires hospitalisation or prolongation of existing inpatient's hospitalisation**;
- Results in persistent or significant disability or incapacity;
- Is a congenital abnormality or birth defect;

Confidential Page 26 of 48

^{* &}quot;Life-threatening" in the definition of "serious" refers to an event in which the participant was at risk of death at the time of the event; it does not refer to an event which hypothetically might have caused death if it were more severe.

^{** &}quot;Hospitalisation" means any unexpected admission to a hospital department. It does not usually apply to scheduled admissions that were planned before study inclusion or visits to casualty (without admission).

London

Medical judgement should be exercised in deciding whether an adverse event/reaction is serious in other situations. Important adverse events/reactions that are not immediately lifethreatening, or do not result in death or hospitalisation but may jeopardise a subject, or may require intervention to prevent one of the other outcomes listed in the definition above should also be considered serious.

Reporting of SAEs (ii)

The primary and secondary outcomes have been selected to capture the most commonly occurring safety events in critically ill patients (e.g. mortality, organ failure and support). Therefore, any events that are captured as an outcome in the eCRF do not require reporting as an SAE unless in the opinion of the local PI the event was attributable to a study intervention / IMP or the trial protocol.

Rapid reporting of all SAEs i.e. within 24 hours, occurring during the patient's ICU stay up to a maximum of 28 days must be performed as detailed in the study-specific safety reporting instructions.

Active monitoring of participants after discharge from ICU or after 28 days is not required, but if the investigator becomes aware of safety information that appears to be drug or trial related, involving a participant who participated in the study, even after an individual participant has completed the study, this should be reported to the Sponsor.

All SAEs will be reviewed by the Chief Investigator or a designated medically qualified representative to confirm expectedness and causality.

Reporting of SAEs and review by the CI will be via the trial data collection system (CRF/eCRF).

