9.4 Adaptive analyses

Regular adaptive analyses will be carried out to monitor the accrued data. Participant baseline characteristics will be summarised by treatment group and overall using suitable descriptive statistics. Adaptive analysis will include formal stopping rules on the primary outcome which will be triggered by comparing the estimated treatment effect to predefined efficacy and futility boundaries. Summary and between-intervention statistics for secondary and safety outcomes will be presented by treatment group.

The first adaptive analysis will take place at the end of the calendar month when the cumulative number of participants recruited into the larger (hypoinflammatory) subphenotype reaches 240, i.e. 80 per intervention. Thereafter, adaptive analyses will take place every 3 calendar months unless recruitment varies substantially from the planned recruitment rate, in this case the frequency of the adaptive analysis will be revised. The hypoinflammatory subphenotype will be analysed at every adaptive analysis; the smaller (hyperinflammatory) subphenotype will be included in the regular adaptive analysis when its cumulative recruitment total has reached 240 participants and at alternating analyses thereafter, i.e. every 6 months, unless recruitment varies substantially from the planned recruitment rate.

When a new treatment intervention is added to the hypoinflammatory subphenotype, it will be analysed at the first adaptive analysis when it exceeds 80 recruits and at every analysis thereafter until stopping. When a new treatment intervention is added to the

Confidential Page 30 of 48

hyperinflammatory subphenotype, it will be analysed at the first analysis when it exceeds 80 recruits and at alternate analyses thereafter until stopping. The threshold of 80 recruits was chosen to maximise the potential for early stopping (and hence the efficiency of the platform) while also limiting type I error rates, which are higher in smaller samples.

Recruitment to a treatment group within a given subphenotype will be halted when an analysis reveals that an efficacy or futility boundary has been breached, or when the sample size cap is reached or at the discretion of the DMC based on wider review of the trial data. At this point, a final analysis of that treatment within subphenotype with respect to all outcomes will be carried out. After a treatment is stopped a new treatment intervention within that subphenotype may be initiated.

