At the first adaptive analysis, confirmation of the validity of the proportional odds assumption will be carried out in each subphenotype. This will be based on the observed distribution of the primary outcome ordinal scale in each treatment intervention compared to usual care. If the proportional odds assumption is not met, then alternative categorisations (i.e. grouping some categories in the ordinal scale together) will be explored. For all adaptive analysis we will examine the consistency of the unadjusted between-group treatment effect across the composite outcome elements (death and organ support free days) for each comparison within each subphenotype.

Very little missing data are expected for the primary outcome; we anticipate minimal loss to follow-up, and eCRFs will be designed so that recording of primary outcome data is mandatory. If the level of missingness does not exceed 5% then the missing data will be assumed to be ignorable, i.e. a complete case analysis will be carried out. If over 5% of outcome data are missing, then the missingness pattern and relationship to other variables will be explored and multiple imputation will be performed.

Statistical stopping triggers

The criteria for stopping recruitment to a treatment group within either subphenotype are based on the probability that the unadjusted odds ratio crosses a predefined value by a predetermined probability threshold. The initial triggers for stopping were identified through extensive simulations to optimise the trial operating characteristics and achieve an appropriate balance between the sample size needed, maximising the power to graduate treatments exceeding the minimal clinically important effect and minimising the chance of graduating treatments with no effect (type I error).

Stopping recruitment to a treatment within either subphenotype will be considered if any of the following conditions are met at any adaptive analysis:

- For efficacy if there is at least an 84% probability of the proportional odds ratio exceeding 1.1.
- For futility if there is at least a 78% probability of the proportional odds ratio falling below 1.075.

These are considered non-binding stopping rules as the DMC will also take into consideration information presented on other outcomes including safety and recruitment data.

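### Two safety outcomes in Protocol Section 3.5 are badly defined: serious infection joins two infections by *and*, and a GI bleed counts only if seen at endoscopy

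*Protocol*

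**What the plan says.** Protocol Section 3.5 lists the safety outcomes under item viii. Two of them matter here.

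- **Serious infection:** "Serious infection defined as a positive blood cultures requiring treatment and pulmonary aspergillosis requiring treatment".
- **Clinically important GI bleeding** is worded as follows: "Defined as overt bleeding on GI endoscopy, developing as a complication in the ICU and accompanied by 1 or more of the following features". The four features, assessed within 24 hours, are a 20 mmHg pressure drop, a vasopressor start or 20% increase, a haemoglobin fall of at least 2 g/dl, and transfusion of at least two units.

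The liver item in the same list is worded with *or*: "Alanine Transaminase or Aspartate Transaminase more than 8 times the upper limit of normal".

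On use, Section 9.4 says of the adaptive analyses: "Summary and between-intervention statistics for secondary and safety outcomes will be presented by treatment group". It makes the stopping rules non-binding because "the DMC will also take into consideration information presented on other outcomes including safety and recruitment data".

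On other routes of capture, Section 8.8 says that "any events that are captured as an outcome in the eCRF do not require reporting as an SAE" unless the local investigator attributes the event to the intervention or the protocol. Section 8.6 says that "events related to the underlying critical illness will not be reported as adverse events".

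**The concern.** Both outcomes are current protocol text, so this is not a detail left to the SAP.

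For infection, a site that follows the sentence literally would not record candidaemia alone or aspergillosis alone. A site that reads it as a list would record both. The trial recruits at many sites in several countries, so the same patient could be classified differently at two of them.

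For GI bleeding, a patient with melaena, a 2 g/dl haemoglobin fall and a two-unit transfusion meets two listed features but is not an event without endoscopy. Section 6.3 makes the trial open-label with an unmasked clinical team. Endoscopy is absent from the visit schedule in Section 6.4, and Section 7.2 leaves decisions outside the protocol to the treating clinician. Whether a bleed counts can therefore depend on a choice made with knowledge of the allocation. That fits poorly with the assurance in Section 6.3 that most secondary outcomes are objective and unaffected by such knowledge.

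Section 2 justifies using drugs outside their licensed indications partly on the ground that safety monitoring is adequate. The DMC sees these outcomes by arm, so what they count should be clear.

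**Working it through.** The protocol states no event rate, endoscopy rate or power for any safety outcome, so there is no figure to reproduce. The finding rests on the wording. **Every rate below is an assumption that shows scale only.**

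**1. Infection: the two readings.** Let *b* be the proportion with treated positive blood cultures and *a* the proportion with treated pulmonary aspergillosis. Under independence:

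- both required: *ab*
- either suffices: *a + b − ab*
- share of events kept by the strict reading: *ab / (a + b − ab)*

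If every aspergillosis patient also had positive cultures (the largest possible overlap when *a* < *b*), the share kept is *a / b*.

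| *b* | *a* | Both | Either | Share kept, independent | Share kept, full overlap |
|---|---|---|---|---|---|
| 5% | 2% | 0.1% | 6.9% | 1% | 40% |
| 10% | 5% | 0.5% | 14.5% | 3% | 50% |
| 20% | 10% | 2.0% | 28.0% | 7% | 50% |

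Under the list reading nothing is lost. The consequence therefore turns on one word that the protocol leaves open.

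**2. GI bleeding: equal scoping in both arms.** If a fraction *s* of qualifying bleeds is scoped, at most *s* times the true rate is counted. The expected risk ratio is unchanged, but events and precision are lost. Take assumed true rates of 3% v 6%, so *p*₁ = 0.03*s* and *p*₂ = 0.06*s*, with *n* per arm, two-sided 5% and 1:1 allocation:

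power = Φ{[*d* − 1.96·SE₀] / SE₁}, where *d* = *p*₂ − *p*₁, SE₀ = √[2*p̄*(1 − *p̄*)/*n*] with *p̄* the mean of *p*₁ and *p*₂, and SE₁ = √[(*p*₁(1 − *p*₁) + *p*₂(1 − *p*₂))/*n*].

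For *n* = 504 and *s* = 1: SE₀ = 0.01306, SE₁ = 0.01302, and (0.03 − 0.0256)/0.01302 = 0.34, so power is 63%. For *s* = 0.5: SE₀ = 0.00934, SE₁ = 0.00933, and (0.015 − 0.0183)/0.00933 = −0.35, so power is 36%.

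| *n* per arm (source) | *s* = 100% | 75% | 50% | 25% |
|---|---|---|---|---|
| 504 (hypoinflammatory cap, Section 4.1) | 63% | 51% | 36% | 20% |
| 529 (hyperinflammatory cap, Section 4.1) | 65% | 53% | 38% | 21% |
| 120 (hypoinflammatory expected mean, Section 9) | 20% | 16% | 12% | 8% |

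The trial's own inference is Bayesian, so these are gauges of lost information and not design properties.

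**3. GI bleeding: unequal scoping.** Observed risk ratio = true risk ratio × (*s* active / *s* usual care). With equal true rates, scoping of 60% v 40% gives 0.60/0.40 = 1.5, and the reverse gives 0.40/0.60 = 0.67. The documents give no reason to expect either direction.

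**4. Can missed events be caught elsewhere?** An unscoped bleed or a single infection that meets the seriousness criteria in Section 8.8 is reportable as an SAE during the ICU stay, up to 28 days. Section 9.6 tabulates SAEs by arm with incidence rate ratios, and by Preferred Term and System Organ Class. Against that, Section 8.6 drops events judged related to the underlying critical illness, and bleeding or infection in the ICU may well be judged so. The backstop exists but is incomplete.

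**The case against.** **The list reading of infection is plausible.** The treatment condition is attached to each infection separately, which suits a list of two qualifying events. Sections 3.5 and 3.6 also use *and* as a list connector elsewhere, as in mortality at two time points. This stands: the defect is an ambiguity, not a definition proven to be narrow. It does not remove the need to settle the wording, since the liver item shows that the same list can mark alternatives with *or*.

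**Requiring endoscopy can be a deliberate choice for specificity.** In critically ill patients a pressure drop or a vasopressor increase has many causes, and bedside reports of bleeding by unmasked staff carry their own bias. This stands in part. It argues for keeping endoscopy-confirmed bleeding as a reported subset, not for making an optional procedure the condition for any event to count.

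**Equal under-counting does not bias the ratio, and small arms have little power anyway.** Both are correct. At 120 per arm, power in the illustration is only 20% even with every bleed scoped, so the definition is not the main limit there.

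**SAE reporting catches what the definitions miss.** It does so in part. An unscoped bleed falls outside the exemption for captured outcomes, so that exemption does not block it, but the exclusion in Section 8.6 can. Intervention-specific appendices may add reporting; they are not shown.

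**A stronger reading is tempting:** that most real events cannot count, or that the open-label design inflates bleeding in one arm. The documents support neither. The first needs an endoscopy rate that is not given, or the strict reading of *and*. The second needs differential scoping, for which there is no evidence.

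**Conclusion.** The point holds as a defect of definition. The infection outcome admits two readings with very different counts. The GI bleeding outcome excludes any unscoped bleed and makes ascertainment depend on an unmasked, discretionary procedure.

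Its size cannot be fixed from the protocol. Under the assumed rates, the strict infection reading keeps 1% to 7% of events if the two infections are independent and 40% to 50% with full overlap; the list reading keeps all of them. For bleeding, the loss is at least the unscoped share, which is unknown, and any bias between arms could run either way. These figures are illustrations and should not be quoted as expected losses.

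The matter is worth correcting because the outcomes are shown by arm at the adaptive analyses and the DMC weighs safety data. It does not touch the primary endpoint or the stopping thresholds.

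**What to change.** 1. **Serious infection:** replace *and* with *or*, and state that either a treated positive blood culture or treated pulmonary aspergillosis counts as an event. Record the two components separately in the eCRF. There is no real downside.
2. **Clinically important GI bleeding:** count overt GI bleeding that develops in the ICU with one or more of the listed features within 24 hours, whether or not endoscopy is done. Record in the eCRF whether endoscopy was done and what it found, and report the endoscopy-confirmed subset by arm alongside the full count.

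The cost is two wording changes and the matching eCRF fields. No new procedure is needed and patient management does not change. The GI change gives up some specificity, because some unscoped bleeds will be of uncertain source; reporting the confirmed subset lets the DMC see how far that matters, and the endoscopy field shows whether scoping differs by arm. Events already collected should be reclassified under the new wording so that sites and analyses stay consistent.
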